The recommended VHA strategy for management of chronic pain involves a stepped approach.¹³ In the stepped care model, most Veterans are managed in primary care, where pharmacological and non-pharmacological treatments are provided as indicated. Although opioids are sometimes prescribed for chronic pain, a recent RCT compared opioids to non-steroidal anti-inflammatory drugs among Veterans with chronic pain and found that outcomes for those treated with opioids were not superior to those treated with nonopioid medications.¹⁴ Prescribing opioids entails risks, including addiction, overdose, fractures, cardiovascular events, bowel obstruction, and cognitive impairment.^{10, 15, 16} Because of these risks, VA Clinical Practice Guidelines recommend against the initiation of opioids for chronic pain and instead recommend the use of self-management strategies and other non-pharmacological treatments, such as Cognitive Behavioral Therapy (CBT).¹⁰ Institute of Medicine guidelines also recommend use of non-pharmacological approaches as standard of care for chronic pain before prescribing opioids.¹⁷ Similarly, the American College of Physicians guidelines for treatment of chronic low back pain recommend non-pharmacological therapies as initial treatment, and list CBT and Mindfulness-Based Stress Reduction (MBSR) as options that should be offered as standard care.¹⁸

Psychological interventions have been advocated as non-pharmacological therapies for chronic pain based on evidence that psychological processes play key roles in pain outcomes. Depression, pain catastrophizing, and

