3.0 Objectives

The Primary Aim of this study is to determine whether MBSR and CBT-CP each result in greater reductions in the pain interference subscale of the Brief Pain Inventory (BPI) as compared to usual care, from baseline to 6 months post-treatment for Veterans with Chronic Musculoskeletal Pain.

Hypothesis: Veterans with chronic pain randomized to each active intervention (MBSR or CBT-CP) will report changes in BPI pain interference that are each superior to usual care, from baseline to 6-month follow-up.

Secondary Aim: Evaluate if MBSR and CBT-CP are each superior to usual care in producing improvements in pain severity, treatment satisfaction, and depression. **Exploratory Aim 1:** Evaluate whether outcomes for patients randomized to MBSR and CBT-CP differ for changes in pain interference, pain severity, depression, and treatment satisfaction. **Exploratory Aim 2:** Evaluate the impact of MBSR and CBT-CP on utilization of opioid analgesics and markers of suicidality. **Exploratory Aim 3:** Evaluate moderators of response to MBSR and CBT-CP to lay the groundwork for identifying Veterans more likely to succeed in one or the other treatment. Potential moderators assessed will include: age,

gender, baseline depressive symptoms, anxiety sensitivity, and pain catastrophizing

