Recruitment will occur via the following mechanisms: a). IRB- approved Informational flyers distributed at both campuses on VA Puget Sound research kiosks, hospital health fairs, hallway information tables and bulletin boards; at presentations by investigators; and via emails to clinicians and staff; b) Provider referral from VA outpatient clinics as a result of informational inservices and email announcements for VA providers, which will include Primary Care, Specialty Care (e.g., Rheumatology), Rehabilitation Medicine and the Pain Service clinics, Mental Health, and others. Providers will be given detailed information about study inclusion/exclusion criteria, recruitment process, and treatment goals. If needed to increase recruitment, study staff may also attend team meetings in relevant clinics to increase awareness of the study. Providers can refer Veterans by either alerting study staff in CPRS, via an encrypted VA email or TEAMS, via phone call, or in-person. We will ask providers to include both the contact information of the potential participant as well as confirmation that the Veteran verbally agreed to be contacted by the research study; c) Sending informational letters to patients referred to MBSR or the Pain Service for clinical care, which ask if they are interested in participating in the study; d) Sending letters to Veterans who have received care at VA Puget Sound who have had a clinical encounter with a musculoskeletal disorder ICD10 code identified via a VINCI data pull: M05-M19,M21-M25,M30-M36, M40-M43, M45-M49, M50-M54, M60-M63, M65-M67,M70-M79, L40.5. We will also use VINCI to eliminate from this list Veterans with diagnoses that would make them ineligible- Dementia, Schizophrenia, Borderline Personality Disorder or Anti-Social Personality Disorder. If the Veteran does not respond to the letter, he/she may receive up to 3 phone calls about the study to assess level of interest. (We have two recruitment letters for this study- one prompting the Veterans to call us if interested, and one stating that the Veteran may receive up to 3 calls. We have found in the past that study interest wanes over time, so we have given ourselves the flexibility to use an opt-out method with calling if necessary for later study Cohorts.) The strategy of sending letters to patients with pain codes has been highly effective in a prior trial conducted by our team; this has met with IRB approval. Veterans who are referred to the trial or respond to the letter or phone call indicating interest will undergo telephone assessment of inclusion/exclusion criteria. If eligible by telephone screening, consent forms will be mailed to the Veteran, and a phone appointment will be scheduled to consent the Veteran by phone. The

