
Veteran will return these signed consents in a prepaid envelope. Once they are received by study staff, a phone baseline visit will be scheduled to fully assess eligibility and obtain informed consent. Using this method, in our trial of MBSR for Gulf War Illness (see preliminary studies) approximately 4% of Veterans with chronic pain diagnoses who received a letter followed by a telephone call were successfully randomized. We plan to duplicate this method of recruitment for the proposed trial. Extrapolating to this proposal, we estimate that sending out 5,550 letters and making 5,550 telephone calls over 27 months of recruitment will result in successful recruitment of at least 222 Veterans with chronic musculoskeletal pain. Our experience has shown us that this number of phone calls takes approximately 2 hours of staff time per day. Thus, the recruitment goals are very feasible using these methods. As shown below in Table 1, chronic pain is very common; we expect that the large number of Veterans at our site potentially eligible for enrollment will lead to an adequate number of Veteran enrollees.

Conditions Included	No. of Patients With 1+ Outpatient Visits and 1+ Pain Musculoskeletal Condition
Musculoskeletal conditions included: ICD10 codes: M05-M19,M21-M25,M30-M36, M40-M43, M45-M49, M50-M54, M60-M63, M65-M67,M70-M79, L40.5 (arthropathies, osteoarthritis, other joint disorders, connective tissue disorders, dorsopathies, spondylopathies, myopathies, disorders of synovium and tendons, shoulder lesions, bursopathies, soft tissue disorders, arthropathic psoriasis)	41,033

Participants will paid \$45 for baseline, \$60 for the post-assessment, and \$75 for the 6-month after intervention follow-ups. The maximum remuneration is \$180 if randomized. Subject payments will be processed within a week of the assessment to which they apply.

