5.4 Inclusion/Exclusion Criteria

Inclusion criteria: All participants must meet criteria for chronic musculoskeletal pain, defined as: 1) musculoskeletal pain of low back, cervical spine, or extremities (hip, knee, or shoulder) 2) pain for at least 3 months; and 3) Pain severity (worst or average pain score ≥ 4)(i.e., score of 4 or greater on BPI items 3 or 5) and average pain interference (BPI items 9A-9G) rated ≥ 3 of 10 over prior week, as measured using the Brief Pain Inventory (BPI).^{19, 37, 70}

Exclusion criteria: At phone screen, researchers will check medical records for a diagnosis of schizophrenia, dementia, antisocial personality disorder, or borderline personality disorder. Researchers will also exclude anyone with a flag in their medical record that indicates they are at high risk of suicide or homicide. Veterans will also be excluded if there is mention of psychotic symptoms in any recent treatment notes, or if there is an inpatient admission for psychiatric reasons in the past month. Veterans will be excluded if they endorse attempts to harm themselves or someone else in the past 30 days. Veterans will be excluded if they endorse severe medical conditions that would limit participation (e.g., Class III or IV heart failure) or pending back surgery that would occur during study participation. Additional exclusion criteria include prior formal participation in MBSR or CBT-CP, and

lack of access to internet and the technology needed to participate in a telehealth group.

At baseline, the MINI psychiatric interview²⁶ will determine psychiatric exclusion criteria: 1) uncontrolled psychotic disorder; 2) current bipolar affective disorder with mania; 3) moderate or higher suicide risk 4) use of drugs (besides marijuana or alcohol) more than once in the past 3 months. We will include subjects with Alcohol Use Disorder (AUD; defined by the MINI) but exclude those for whom alcohol use poses a safety threat (defined as current drinking and a past-year history of alcohol-related seizures or delirium tremens). We will also include those with Opioid Use Disorder (OUD) and other Substance Use Disorder (SUD; each defined by the MINI). Medication, supportive individual or group counseling, case management, and self-help programs will be allowed and assessed as potential covariates.

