OME Opioid Use Tracking	B, P, 6		Opioid Use
VA mental health care			
VINCI data pull			Opioid use, prescription sleep medication use, other care (visits for pain, pain-related procedures), markers of suicidality (high-risk suicide flag, psychiatric admissions, deaths due to suicide)
CPRS review for engagement in other treatments	8-months post-baseline	dichotomous	Other care received during study

Full text of measures in appendix.

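### Veterans already referred to clinical MBSR can be enrolled and allocated to usual care, and nothing in the plan addresses MBSR taken off study, which would shrink both primary contrasts

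*Combined protocol and SAP*

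**What the plan says.** Section 5.2 (Recruitment Methods) gives four routes. Route (c) is "Sending informational letters to patients referred to MBSR or the Pain Service for clinical care". Route (d) is a mailing to Veterans with a musculoskeletal diagnosis code. The projection in the same section is that "sending out 5,550 letters and making 5,550 telephone calls over 27 months of recruitment will result in successful recruitment of at least 222 Veterans".

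Section 5.4 deals with exposure to the trial treatments in one clause: "Additional exclusion criteria include prior formal participation in MBSR or CBT-CP". On other care it says "Medication, supportive individual or group counseling, case management, and self-help programs will be allowed and assessed as potential covariates". MBSR and CBT-CP received outside the trial are neither named as allowed nor restricted.

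Section 5.5 plans a "CPRS review for engagement in other treatments" at 8 months after baseline, scored yes/no, and a VINCI data pull covering other care such as visits for pain. Section 5.6 attaches no analysis to either.

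The primary aim in section 3.0 is whether "MBSR and CBT-CP each result in greater reductions in the pain interference subscale of the Brief Pain Inventory (BPI) as compared to usual care". MBSR against CBT-CP is Exploratory Aim 1. The introduction (2.0) cites a low back pain guideline that is said to "list CBT and Mindfulness-Based Stress Reduction (MBSR) as options that should be offered as standard care".

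**The concern.** Route (c) approaches people whom clinicians have already directed to one of the two treatments under test. The exclusion looks backwards only, so a referral not yet acted on does not bar entry. After randomisation, no section reviewed says what becomes of that referral, defines the content of usual care, or addresses MBSR taken outside the trial. The primary assessment comes 6 months after an 8-week treatment period, which leaves time to complete an 8-week course off study.

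Usual care is the comparator in both primary contrasts. Benefit from MBSR received there narrows both differences at once. The sample size makes no allowance for this: section 5.6 assigns its 15% inflation to attrition or clustering.

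**Working it through.** **Inputs (section 5.6).** Difference 1.05 BPI interference points for each active arm against usual care; SD 2.1; two-sided alpha 0.05; power 80%; 64 per arm for the pairwise tests, inflated by 15%.

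**Reproducing the plan.**
- d = 1.05 / 2.1 = 0.50.
- The two-sample t-test (noncentral t) needs 64 per arm for 80% power, as stated; exact power at 64 is 80.1%.
- 64 × 1.15 = 73.6, rounded up to 74 per arm, and 3 × 74 = 222, as stated.
- If all 74 per arm were evaluable, power would be 86%.

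**Effect of crossover.** Let c be the share of the usual-care arm that receives MBSR off study. Assume that each of them gets the full 1.05-point benefit. The usual-care mean then improves by 1.05 × c. Because the plan assumes the same effect for both active arms, each primary contrast becomes

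difference = 1.05 × (1 − c), so d = 0.50 × (1 − c).

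Power follows from the noncentral t with noncentrality d × √(n/2) and 2n − 2 degrees of freedom.

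| c (assumed) | Difference | d | Power, 64 per arm | Power, 74 per arm |
|---|---|---|---|---|
| 0 | 1.05 | 0.500 | 80% | 86% |
| 2.5% | 1.02 | 0.488 | 78% | 84% |
| 5% | 1.00 | 0.475 | 76% | 82% |
| 10% | 0.945 | 0.450 | 71% | 78% |
| 20% | 0.84 | 0.400 | 61% | 68% |

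The evaluable number per arm needed for 80% power grows roughly as 64 / (1 − c)²: 71 at 5%, 79 at 10% and 100 at 20%. At 10% crossover this already exceeds the 74 randomised per arm.

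**What c depends on.** For crossover that arises from route (c),

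c = (share of the usual-care arm recruited as MBSR referrals) × (share of those who take MBSR up).

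The documents give neither factor. For illustration:
- 10% × 25% = 2.5%
- 10% × 50% = 5%
- 40% × 50% = 20%

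**The CBT-CP arm.** Off-study MBSR in this arm works differently. It enters no primary contrast as dilution. If it adds benefit, it enlarges CBT-CP against usual care, and it blurs MBSR against CBT-CP, which is exploratory.

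**Whether these recruits are needed.** The projection is 5,550 × 4% = 222, based on letters followed by calls to Veterans with pain diagnoses. Table 1 in section 5.2 gives a pool of 41,033, and 41,033 / 5,550 is about 7.4 times the planned mailing. The projection therefore does not rest on route (c).

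**The case against.** **Few may enrol this way.** If the diagnosis-code mailing supplies nearly everyone, crossover from route (c) is small; at 2.5% the loss is about 2 percentage points of power. Route (c) also includes Pain Service referrals, which are not MBSR referrals. Late starters and poor attenders would not get the full benefit assumed in the table. This stands, and it limits how firmly any size can be stated.

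**Usual care may be meant to include clinical MBSR.** Section 5.1 calls the study a comparative effectiveness trial, and the introduction presents MBSR as a standard-care option. On that reading the diluted difference is the pragmatic answer, not a bias. The argument is fair but incomplete: the plan already excludes earlier MBSR or CBT-CP, does not say that usual care includes either, and makes no visible allowance for it in the 1.05-point difference or the 15% inflation.

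**There are partial safeguards.** The CPRS review and VINCI pull can show other care received, and co-treatments may be used as covariates. These record crossover but do not prevent it, and no analysis of it is specified.

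**Stronger readings that the documents do not support.** A reader might infer that off-study MBSR in the CBT-CP arm also dilutes a primary contrast; section 3.0 rules that out. A reader might infer that these Veterans hold open referrals or booked places; section 5.2 says only that they were referred, and some referrals may have lapsed or been declined. A reader might also expect usual-care participants to score worse out of disappointment; that is speculation and would apply to any unblinded usual-care arm.

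The parts of the text between sections 1.0 and 2.0 and between 3.0 and 5.0 (by the contents list, personnel and resources) and the consent forms were not available. A rule placed there cannot be excluded, though it would be an unusual place for one.

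**Conclusion.** The gap is real. As written, the plan can enrol a Veteran already referred to clinical MBSR, allocate that Veteran to usual care, and leave MBSR open to them before the 6-month assessment. The consequence is a smaller expected difference in both primary contrasts.

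The size cannot be determined. Across assumed crossover of 2.5% to 20%, power is 78% to 61% with 64 evaluable per arm, or 84% to 68% with 74. These figures rest on the plan's own effect and SD and on full benefit in every crossover, so they lean toward the larger loss. The low end is plausible, given the reliance on diagnosis-code letters. The point justifies a short amendment; it does not show that the trial is underpowered.

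Nor do the documents require that the MBSR-referral letters be abandoned. Dropping them would not stop Veterans recruited by other routes from being referred to MBSR later, whereas an eligibility rule applies to every route at entry.

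**What to change.** 1. In 5.4, extend the existing exclusion to cover current enrolment in clinical MBSR or CBT-CP, or a referral to either that the Veteran plans to take up during the study period. Check it at the phone screen, where the medical record is already reviewed.
2. In 5.5, use the planned CPRS and VINCI reviews to record off-study MBSR and CBT-CP by arm. Dates and sessions attended would be more useful than a yes/no entry.
3. In 5.6, keep the as-randomised analysis primary and prespecify a sensitivity analysis for off-study receipt.
4. Optionally, drop MBSR-referred patients from route (c) in 5.2.

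If the sponsor instead intends usual care to include clinical MBSR, the protocol should say so and the 1.05-point assumption should reflect it.

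**Cost.** One extended clause, one extra screening item, fuller coding of a review already planned, and one sensitivity analysis. A few recruits are lost, among them some treatment-seeking Veterans. That slightly narrows generalisability to care-seeking Veterans, a matter that the introduction itself raises. The projection of 222 does not depend on these recruits. The rule does not prevent new referrals after randomisation, which is why items 2 and 3 are needed as well.

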5.3 Informed Consent Procedures

We request a waiver of informed consent for recruitment/screening purposes only. This will allow us to create recruitment mailing lists that can target the most-likely-to-be-eligible populations, and not waste resources

and other patients' time advertising the study to patients who won't be eligible to participate.

We will obtain informed consent prior to beginning any data collection study procedures that will be maintained for analysis. Informed consent will take place prior to the appointment that includes the subject's final eligibility screening and (if still eligible) baseline assessments. The study coordinator, project manager, or other approved researcher will mail or send by docusign interested Veterans consent forms, and obtain informed consent over the phone. We will not enroll anyone with impaired decision-making ability who requires the use of a legally authorized representative.

All study personnel will be trained in human subjects protections requirements as required by R&D (e.g. Privacy Policy & HIPAA training), and the PI or Project Manager will train any other study team members how to appropriately obtain informed consent as needed.

5.4 Inclusion/Exclusion Criteria

Inclusion criteria: All participants must meet criteria for chronic musculoskeletal pain, defined as: 1) musculoskeletal pain of low back, cervical spine, or extremities (hip, knee, or shoulder) 2) pain for at least 3 months; and 3) Pain severity (worst or average pain score ≥ 4)(i.e., score of 4 or greater on BPI items 3 or 5) and average pain interference (BPI items 9A-9G) rated ≥ 3 of 10 over prior week, as measured using the Brief Pain Inventory (BPI).^{19, 37, 70}

Exclusion criteria: At phone screen, researchers will check medical records for a diagnosis of schizophrenia, dementia, antisocial personality disorder, or borderline personality disorder. Researchers will also exclude anyone with a flag in their medical record that indicates they are at high risk of suicide or homicide. Veterans will also be excluded if there is mention of psychotic symptoms in any recent treatment notes, or if there is an inpatient admission for psychiatric reasons in the past month. Veterans will be excluded if they endorse attempts to harm themselves or someone else in the past 30 days. Veterans will be excluded if they endorse severe medical conditions that would limit participation (e.g., Class III or IV heart failure) or pending back surgery that would occur during study participation. Additional exclusion criteria include prior formal participation in MBSR or CBT-CP, and

lack of access to internet and the technology needed to participate in a telehealth group.

At baseline, the MINI psychiatric interview²⁶ will determine psychiatric exclusion criteria: 1) uncontrolled psychotic disorder; 2) current bipolar affective disorder with mania; 3) moderate or higher suicide risk 4) use of drugs (besides marijuana or alcohol) more than once in the past 3 months. We will include subjects with Alcohol Use Disorder (AUD; defined by the MINI) but exclude those for whom alcohol use poses a safety threat (defined as current drinking and a past-year history of alcohol-related seizures or delirium tremens). We will also include those with Opioid Use Disorder (OUD) and other Substance Use Disorder (SUD; each defined by the MINI). Medication, supportive individual or group counseling, case management, and self-help programs will be allowed and assessed as potential covariates.

5.5 Study Evaluations

Study Construct/Variables	Study Phase	Measurement Scale	Domain/Purpose
Inclusion/Exclusion Criteria (eligibility Evaluation)			
MINI International Neuropsychiatric Interview V-5 (DSM-V version) (covers suicidality, mania, alcohol and drug abuse, and psychosis)	B	dichotomous	Sample description, exclusion, SUD classification (possible moderator)
Brief Pain Inventory (BPI) questions 3, 5, and 7a-7g, modified to past week	Phone screen		exclusion
Medical history interview (seizures, DT's)	Phone screen	dichotomous	exclusion
Sample Description Data (to describe subject population)			
Demographic information	B	dichotomous	Sample description, blocking (sex assigned at birth); moderators
Life Events Checklist (LEC)	B	dichotomous	Sample description; Trauma history
Rome IV – IBS	B, 6	Dichotomous	Sample description (indicates current symptoms of IBS)
Anxiety Sensitivity Index	B	Continuous	Sample description,

			moderator
Tracking			
Contact form	B, P, 6		retention
Primary Outcomes			
Pain interference subscale of the Brief Pain Inventory (BPI)	B, P, 6	continuous	Pain interference / physical functioning
Secondary Outcomes			
Pain severity subscale of the Brief Pain Inventory (BPI)	B, P, 6	continuous	Pain intensity
Analgesic use and Underlying pain	B, P, 6	Continuous	Underlying pain intensity
PHQ-9 (depression)	B, P, 6	continuous	Depressive symptoms
PTSD Checklist (Civilian version) (PCL-5)	B, P, 6	continuous	PTSD symptoms
SF-12 (Mental and Physical Component Summary Scores)	B, P, 6	continuous	Sample description; Health-related quality of life (HRQOL)
Five-Facet Mindfulness Questionnaire (FFMQ-15) SF	B, P, 6	continuous	Dispositional mindfulness, and mindfulness subscales: Observing, Describing, Acting with Awareness, Nonjudging and Nonreactivity to inner experiences; potential mediator
Coping Strategies Questionnaire	B, P, 6		Mediator of pain catastrophizing
NIH Patient Reported Outcome Measures Information System (PROMIS) for Alcohol Use and Negative Consequences, short form	B, P, 6	continuous	Substance Use Disorder (SUD) symptom severity for alcohol

NIH Patient Reported Outcome Measures Information System (PROMIS) for Gastrointestinal Distress: Belly Pain, Diarrhea, Constipation, Gas & Bloating	B, P, 6		Gastrointestinal Symptoms, including IBS
Drug Abuse Screening Test (DAST) for drug use other than alcohol or tobacco	B, P, 6	categorical & continuous	Cannabis Use
Client Satisfaction Questionnaire (CSQ-8)	P, 6	continuous	Satisfaction
OME Opioid Use Tracking	B, P, 6		Opioid Use
VA mental health care			
VINCI data pull			Opioid use, prescription sleep medication use, other care (visits for pain, pain-related procedures), markers of suicidality (high-risk suicide flag, psychiatric admissions, deaths due to suicide)
CPRS review for engagement in other treatments	8-months post-baseline	dichotomous	Other care received during study

Full text of measures in appendix.

